#### 6.2.2 Descriptive analyses

The log-transformed quantitative urine measurements of Benzoylecgonine will be summarized by treatment and visit / time and weekly. To obtain the weekly profiles, the BE measurements obtained by a subject during each week (aligned with the weekly profiles of TLFB) will be averaged. These data shall also be listed by subject, and time point.

Descriptive summary tables shall be provided to summarize the alcohol consumption by treatment and week, and by treatment and month. The alcohol daily consumption, weekly consumption and monthly consumption will be listed by subject and time point. If country is a significant effect in the model stated in section 6.2.3 then summary statistics will also be provided by country.

The amount spent on cocaine will be summarized by treatment and listed by subject and time point. The amount spent will be converted in Euros for the summary statistics, using the exchange rates recorded on 7th August 2019 from XE currency converter website (<https://www.xe.com/currencyconverter/convert>). The exchange rates are:

US Dollar to Euro – 0.891

Swiss Franc to Euro – 0.916

Argentine Peso to Euro – 0.019

The number and % of subjects abstinent the last x weeks will be described both on the PD analysis set and FAS.

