2.3 Exploratory objective(s)

Commercially Confidential Information

from cocaine use. For all examinations to be done at baseline, refer to the [Assessment schedule](#).

Treatment (days 1-98): following baseline, on Day 1, approximately 60 eligible patients will be randomly assigned in a 1:1 ratio to either AFQ056 or placebo

- Group A - AFQ056: up-titration regimen for the first 2 weeks (14 days): 50 mg bid from Day 1 to Day 7 , 100 mg bid from Day 8 to Day 14 , followed by dosing at 200 mg bid for 84-days
- Group B: matching placebo.

Study drug: must be taken twice daily (bid) in the morning and evening (separated by approximately 12 hour intervals) with food. For all ambulatory morning visits that involve any study assessments or PK/urine sample collection, study medication will be self-administered by patient at study center and supervised by study personnel. On these days, standard breakfast should be served at study center and consumed by the patient during his/her medication intake.

During treatment period, patients will also undergo assessments with various scales and questionnaires, as well as safety assessments and pharmacokinetic sampling at pre- and 2 ± 1 -hour post dose per SoA. For a detailed outline of all study assessments and time points refer to the [Assessment schedule](#).

Urine samples (days1-113): samples will be collected at study center twice per week, with at least 48 hours separating tests. The sample collection will be assayed quantitatively for the presence of cocaine's metabolite (benzoylecgonine (BE)), as well as, other illicit drugs may be assayed. It is expected that a total of approximately 33 urine samples will be collected during study conduct: 28 samples from patients who remain in treatment for the 14 weeks (total of 4 samples: weeks 1–2 of up-titrations); 24 samples in weeks 3–14 (maintenance dose); 4 samples in weeks 15–16 (follow up) and finally 1 last sample at end of study visit. If a patient fails to attend the clinic or refuses to provide a sample on a scheduled testing day, samples will be considered positive unless an excused absence is granted (e.g.. illness, other personal reason). In cases of missed or refused samples, samples should be collected on the next day whenever possible.

Clinical support to ensure medication and protocol's adherence:

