3.2 Rationale of study design

The design of this trial has been selected to adequately assess the primary objective and follows the similar design of trials for substance use disorders ([American Psychiatric Association \(APA\) Practice Guidelines, 2006](#)). Furthermore, randomized subject and investigator blinded control design are considered as “validated method in stimulant abuse trials” and parallel treatment group design was selected due to the long duration of treatment.

The entire study treatment duration of 98 days will be conducted in an outpatient treatment setting, which is a commonly used setting in treatment of substance use disorders ([UNODC-WHO, 2016](#)) and appropriate for the purpose of this study. The outpatient setting in this study includes frequent visit schedule (twice/week) in conjunction with urine sample collection; weekly monitoring of medication and study assessment adherence and safety adverse event monitoring. As an outpatient setting may increase the likelihood of patients dropping out of treatment, weekly interventions of Positive Reinforcement techniques are introduced with the focus on patient's adherence to the protocol's procedures and medication compliance.

For primary objective, daily cocaine use will be determined using TLFB self-report, which is a "gold standard" for measurement of substance use ([Robinson et al 2012](#)). For secondary objective, cocaine use will be determined twice/week by urine drug screen

Commercially Confidential Information Frequency of urine sample collection was scheduled in accordance with the halflife of cocaine metabolites BE in urine (3-4 days).

Commercially Confidential Information

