4.1 Inclusion criteria

CUD patients eligible for inclusion in this study must fulfill **all** of the following criteria:

1. Understand the study procedures and provide written informed consent before any assessment is performed.
2. Male and female subjects, 18 to 65 years of age (inclusive) and diagnosed with Cocaine Use Disorder according to DSM 5 (Diagnostic and Statistical Manual of Mental Disorders, 5th Ed.).
3. Must use cocaine through snorting (intranasally), as primary route of administration.

4. Recent cocaine use confirmed by positive urine screen for 1 or more benzoylecgonine (BE).
5. Must be seeking treatment for cocaine dependence and have a desire to reduce or cease cocaine use as per goals assessed at baseline.
6. Must be abstinent from cocaine use for at least 3 days preceding 1st dosing (Day 1) as assessed by self-report TLFB. The two urine drug screen samples at v2 and v3 must show a decrease in BE level or both must be negative.
7. Must be in good health as determined by medical history, physical examination, at screening.
8. At screening and baseline, vital signs (systolic and diastolic blood pressure and pulse rate) must be within the acceptable ranges by the investigator considering the cocaine's increasing effect on pulse rate in order for the subject to qualify. The investigator may be guided to use the below ranges:
 - systolic blood pressure, 90-150 mmHg
 - diastolic blood pressure, 50-90 mmHgThree readings are acceptable. At least the one of three readings must be within the acceptable ranges.
9. Patients must be able to:
 - communicate well verbally with the Investigator and to understand written instructions.
 - verbalize a willingness to complete all study procedures.
 - verbally acknowledge that she/he will be able to attend each scheduled visit, and that she/he does not have any already scheduled events or activities that may substantially interfere with study participation.

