11.4.1 Primary Variable(s)

The primary variable is the proportion of cocaine use days during the treatment period (days 1-98).

For each patient, the proportion of cocaine use days will be calculated by dividing the number of days of cocaine use during the treatment period, i.e. 98 days for completers and number of days between Day 1 and day of last dose in case of premature discontinuation of study treatment. It is considered as a continuous variable with a normal distribution. The cocaine consumption will be recorded daily (Yes/No) using the TLFB during the entire study.

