11.5.1 Efficacy / Pharmacodynamics

11.5.1.1 Measure of cocaine in (BE) in urine

Two urine samples per week will provide a quantitative measure of cocaine's metabolite BE. The proportions of positive urine samples over the treatment period will be compared between groups using a t-test.

The quantitative BE profiles over time will be explored using visualization techniques and compared between groups using models appropriate to the distribution of the data.

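### Urine BE is grouped by collection date rather than by the days it reports on: Day 1 counts as treatment, Day 99 as follow-up, and weekly BE means lag weekly TLFB

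*SAP*

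**What the plan says.** The urine paragraph of the protocol's study design text, just before section 3.2, sets collection at twice per week and states: "It is expected that a total of approximately 33 urine samples will be collected during study conduct". It divides these into "28 samples from patients who remain in treatment for the 14 weeks" (4 in weeks 1-2 and 24 in weeks 3-14), then "4 samples in weeks 15–16 (follow up) and finally 1 last sample at end of study visit". An unexcused missed or refused sample is counted as positive.

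Table 8-1 places the treatment-epoch urine screens at visits 101-128, nominally Days 1, 4, 8, 11 and so on to 92 and 95. The urine row is blank at visit 199 (Day 98). The next urine is at visit 201 (Day 99), in the follow-up epoch. Every one of these visits except Day 1 has a window of ±1 day.

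Protocol 3.2 ties the sampling frequency to the half-life of BE in urine, given as 3-4 days. Protocol 11.5.1.1 plans the period analysis: "The proportions of positive urine samples over the treatment period will be compared between groups using a t-test". Protocol 11.4.1 takes the treatment period as Days 1-98.

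For weekly summaries, SAP 6.2.2 says that "the BE measurements obtained by a subject during each week (aligned with the weekly profiles of TLFB) will be averaged". The same section also summarises BE by visit.

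**The concern.** TLFB assigns cocaine use to the day on which it happened. A urine sample reports on the days before it was taken, and the protocol's own reason for the sampling frequency relies on this. Grouping both measures by the same study week therefore puts different days side by side.

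The mismatch matters most at the edges. The Day 1 urine is taken at the visit where dosing starts, so it reflects pre-treatment use. That use is also selected, because Protocol 4.1 requires at least 3 days of self-reported abstinence before Day 1. At the other end, the last days at the maintenance dose are seen only in a sample labelled follow-up. BE is the only objective measure of cocaine use in the visible objectives table (Protocol 2.2), beside a self-reported primary, so its periods and weeks should mean what they appear to mean.

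**Working it through.** **1. Reproduce the plan's count.** Treatment urines fall on Days 7w-6 and 7w-3 for w = 1 to 14, which gives 2 × 14 = 28. Follow-up urines fall on Days 99, 102, 106 and 112, which gives 4. With one at end of study, 28 + 4 + 1 = 33, as stated. The split into 4 and 24 works only if Day 1 is in week 1 (Days 1, 4, 8, 11). The follow-up count of 4 works only if Day 99 is a follow-up sample.

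**2. Weight of the Day 1 sample.** For a completer it moves the proportion positive by at most 1/28 = 3.6 percentage points. If the arms differ by d on the other 27 samples and by nothing on Day 1, the expected difference is (27 × d + 0)/28 = 0.964d. For a patient who stops at Day 14 the weight is 1/4 = 25%; at Day 28 it is 1/8 = 12.5%. In the Week 1 mean (Days 1 and 4) it is 1/2.

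**3. Gap at the end.** The last treatment urine is on Day 95 and the next on Day 99. Use on Days 96-98 therefore cannot appear in any of the 28.

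**4. Weekly means.** Assume TLFB weeks of Days 1-7, 8-14 and so on. This is inferred: the protocol equates weeks 1-2 with up-titration, which is Days 1-14. The first sample of each week falls on Day 7w-6, its first day, so 14 of 28 samples (50%) do.

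The documents give no detection window, so I took a range. The table shows the share of each look-back that falls before the assigned week, with the sampling day excluded. Under exponential decay with half-life h and constant daily use, the share of a sample's signal from more than n days back is 2^(-n/h).

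| Assumed look-back | First sample | Second sample | Weekly mean now | Weekly mean re-paired (Days 7w-3, 7w+1) |
|---|---|---|---|---|
| 3 days | 100% | 0% | 50% | 0% |
| 4 days | 100% | 25% | 62.5% | 12.5% |
| Half-life 3 days | 100% | 2^(-3/3) = 50% | 75% | (50% + 2^(-7/3))/2 = (50% + 19.8%)/2 = 34.9% |
| Half-life 4 days | 100% | 2^(-3/4) = 59.5% | 79.7% | (59.5% + 2^(-7/4))/2 = (59.5% + 29.7%)/2 = 44.6% |

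A 2-day look-back gives the same present figure as 3 days, 50%.

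If the sampling day is counted within a 2- to 4-day look-back, the present share is 25% to 37.5%. Re-pairing then replaces earlier use with a smaller or equal share of later use: (1/2 + 0)/2 = 25% at 2 days and (1/4 + 0)/2 = 12.5% at 4 days. The study design text describes urine visits as morning visits, so excluding the sampling day is closer to practice.

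These are shares of look-back, not predicted changes in BE concentration.

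**The case against.** The case for leaving the rule alone has real substance.

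- SAP 6.2.2 also summarises BE by visit, and Protocol 11.5.1.1 plans quantitative profiles over time. Onset and the dose steps can be read there without any weekly grouping. This stands, and it confines the lag to the weekly summary.
- The visible text never states on which day a TLFB week starts. The inference from the dosing days is reasonable but remains an inference. The ±1 day windows also mean that a Day 8 visit may be held on Day 7.
- The sample counts describe collection, and the period comparison lists no visits. That Day 1 enters the tested proportion follows from reading the 28 treatment samples together with a treatment period of Days 1-98. SAP 6.2.3, which holds the urine model, is redacted and may say more. It would still leave the weekly averaging stated in 6.2.2.
- The rule is identical in both arms, and the Day 1 weight is small. This stands.
- Re-pairing is not a complete cure. Under the stated half-life taken literally, about 35-45% of the weekly mean would still reflect earlier use. Moving Day 99 into treatment also brings risks of its own: a skipped follow-up visit could become an imputed on-treatment positive, and a visit on Day 100 could include post-treatment use.

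These points limit the size of the concern and shape the remedy. They do not explain why a pre-treatment sample should count as treatment.

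**Conclusion.** The point holds at modest size. Grouping by collection date puts a pre-treatment sample among the 28 treatment samples, leaves use on Days 96-98 to a follow-up sample and, if TLFB weeks start on Day 1, makes the weekly BE profile lag the TLFB profile. The consequences are a dilution factor of 27/28 in the period proportion (more weight for early stoppers) and a blurred weekly table. The exact lag depends on a look-back that the documents do not give.

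A reader might infer more, and the documents do not support it:

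- That half of the weekly BE values belong to the previous week. Each weekly value averages one sample mainly about the week before with one mainly about the current week.
- That the treatment comparison is biased. Both arms follow the same rule, and the TLFB primary does not use urine.
- That agreement between BE and TLFB will be understated. No visible analysis estimates agreement.

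A change to the SAP is still worthwhile, because it costs almost nothing and improves a secondary endpoint.

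**What to change.** 1. Define visit 101 (Day 1) as baseline. Exclude it from the treatment-period proportion of positive samples and from the Week 1 mean.
2. State the first day of a TLFB week, and form weekly BE by nominal visit: for week w, the samples scheduled for Days 7w-3 and 7w+1. Week 1 then uses Days 4 and 8, and Week 14 uses Days 95 and 99. Using nominal visits also stops the ±1 day window from moving a sample across a week boundary.
3. Include visit 201 (Day 99) in the treatment-period endpoint only when a sample was actually provided, never when it is missing and imputed positive. The maximum stays at 28 samples (27 + 1). Note that a sample taken on Day 100 may contain up to about 2 days of post-treatment use.
4. For patients who stop early, add no sample after the last dose. The documents give no look-back on which to base a window, and Protocol 7.2 schedules their visit about 1 week after the last dose.
5. Align the sample counts in the protocol's study design text with this assignment, and say in the SAP that re-pairing reduces the lag without removing it.

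The cost is SAP wording and a revised visit-to-week map in programming. No visits or samples are added.

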### **6.2.3 Statistical model, assumptions and hypotheses**

Commercially Confidential Information

#### **6.2.3.1 Model checking procedures**

Commercially Confidential Information

#### **6.2.3.2 Graphical presentation of results**

Commercially Confidential Information

## **6.3 Exploratory objectives**

### **6.3.1 Variables**

Commercially Confidential Information

Commercially Confidential Information

### **6.3.2 Descriptive analyses**

Commercially Confidential Information

### **6.3.3 Statistical model, assumptions and hypotheses**

Commercially Confidential Information

### **6.3.4 Graphical presentation of results**

Commercially Confidential Information

## **7 Statistical methods for safety and tolerability data**

### **7.1 Variables**

Adverse events, vital signs (blood pressure, pulse rate, body temperature), ECG intervals, laboratory measurements, as well as subject demographics, baseline characteristics, and treatment information.

## 7.2 Descriptive analyses

### Subject demographics and other baseline characteristics

All data for background and demographic variables will be listed by treatment group and subject. Summary statistics will be provided by treatment group.

Relevant medical history, current medical conditions, results of laboratory screens, drug tests and any other relevant information will be listed by treatment group and patient.

### Treatment

Data for study drug administration (rescue medication) and concomitant therapies will be listed by treatment group and patient.

### Vital signs

All vital signs data will be listed by treatment, subject, and visit/time and if ranges are available abnormalities (and relevant orthostatic changes) will be flagged. Summary statistics will be provided by treatment and visit/time.

### ECG evaluations

All ECG data will be listed by treatment, subject and visit/time, abnormalities will be flagged. Summary statistics will be provided by treatment and visit/time.

### Clinical laboratory evaluations

All laboratory data will be listed by treatment, subject, and visit/time and if normal ranges are available abnormalities will be flagged. A separate listing is provided presenting all parameters in a subject with any abnormal values. Summary statistics will be provided by treatment and visit/time. Newly occurring liver enzyme abnormalities will be listed by treatment, subject and visit/time.

### Adverse events

All information obtained on adverse events will be displayed by treatment and subject.

The number and percentage of subjects with adverse events will be tabulated by body system and preferred term with a breakdown by treatment. A subject with multiple adverse events within a body system is only counted once towards the total of this body system and treatment.

For the legal requirements of ClinicalTrials.gov and EudraCT, two required tables on <on-treatment/treatment emergent> adverse events which are not serious adverse events with an incidence greater than X% and on <on-treatment/treatment emergent> serious adverse events and SAE suspected to be related to study treatment will be provided by system organ class and preferred term on the safety set population.

If for a same subject, several consecutive AEs (irrespective of study treatment causality, seriousness and severity) occurred with the same SOC and PT:

- a single occurrence will be counted if there is  $\leq 1$  day gap between the end date of the preceding AE and the start date of the consecutive AE
- more than one occurrence will be counted if there is  $> 1$  day gap between the end date of the preceding AE and the start date of the consecutive AE.

For occurrence, the presence of at least one SAE / SAE suspected to be related to study treatment / non SAE has to be checked in a block e.g., among AE's in a  $\leq 1$  day gap block, if at least one SAE is occurring, then one occurrence is calculated for that SAE.

The number of deaths resulting from SAEs suspected to be related to study treatment and SAEs irrespective of study treatment relationship will be provided by SOC and PT.

### **Other safety evaluations**

The Columbia Suicide Severity Rating Scale data will be listed by treatment group, subject and visit.

### **7.3 Graphical presentation**

Boxplots to visualize trends in longitudinal safety data (vitals, ECG, lab parameter) will be created.

Commercially Confidential Information
